## Appendix B: Inhalation Training with In-Check DIAL

The In-Check DIAL is an inhalation airflow meter that can help educate and assess patients who use inhaler devices. It simulates the internal resistance of several common inhaler devices, and measures inspiratory flow. Inspiratory flow rate measurements will be obtained at screening and visits 2, 3, and 4 using the In-Check DIAL device.

### How to use the In-Check DIAL

[figure not shown]
1. Reset the In-Check DIAL. The cursor should be reset to zero through a “tap and turn” maneuver which releases a seated magnet from the top of the DIAL and pushes the cursor back. The DIAL should then be turned upside down to reseat the magnet so as not to get in the way of an accurate measurement.

[figure not shown]
2. Align the scale with the inhaler device. With the triangular pointer on top of the scale, align the “dial” portion of the device for use with HANDIHALER adapter by setting the device to no resistance circle (pMDI) icon - an audible "click" should be heard.

[figure not shown]
3. Attach a clean mouthpiece. Attach the HANDIHALER resistance adapter (blue transparent cylinder provided separately in a sealed plastic bag) to mimic SPIRIVA HANDIHALER resistance. Insert a disposable one-way valved inspiratory mouthpiece into the wider end of the blue transparent adapter.

[figure not shown]
4. Ask the patient to exhale slowly and fully.

5. Seal lips around the mouthpiece. According to the inhaler setting (no resistance circle [pMDI] icon) and HANDIHALER resistance adapter), instruct the patient to inhale deeply.

6. Record the inspiratory flow from the position of the red cursor against the scale. Reset, and repeat until 3 successful inspiratory flow rates ( $\geq 40$  L/min) are achieved. Record the three (3) inspiratory flow rates on the patient's source.

## Appendix C: EXACT DAILY DIARY

**Instructions:** Please complete your diary every evening, just before you go to bed. As you answer the following questions, please select the option that best describes your experience.

The diary will be programmed to display your ER-S: COPD daily respiratory symptoms (RS) Total score. A baseline score will be obtained from the first available evening session after the screening visit (visit 1) for use during the screening and run-in periods and from the latest available evening session before the randomization visit (visit 2) for use during the double-blind and open-label treatment periods. If at any time, there is increase in the daily RS Total score of  $\geq 2$  from baseline, the diary will alert you to notify investigational center personnel to discuss your current health status.

1. Did your chest feel congested today?	Not at all
	Slightly
	Moderately
	Severely
	Extremely
2. How often did you cough today?	Not at all
	Rarely
	Occasionally
	Frequently
	Almost constantly
3. How much mucus (phlegm) did you bring up when coughing today?	None at all
	A little
	Some
	A great deal
	A very great deal
4. How difficult was it to bring up mucus (phlegm) today?	Not at all
	Slightly
	Moderately
	Quite a bit
	Extremely
5. Did you have chest discomfort today?	Not at all
	Slight
	Moderate
	Severe
	Extreme

6. Did your chest feel tight today?	Not at all
	Slightly
	Moderately
	Severely
	Extremely
7. Were you breathless today?	Not at all
	Slightly
	Moderately
	Severely
	Extremely
8. Describe how breathless you were today:	Unaware of breathlessness
	Breathless during strenuous activity
	Breathless during light activity
	Breathless when washing or dressing
	Present when resting
9. Were you short of breath today when performing your usual personal care activities like washing or dressing?	Not at all
	Slightly
	Moderately
	Severely
	Extremely
	Too breathless to do these
10. Were you short of breath today when performing your usual indoor activities like cleaning or household work?	Not at all
	Slightly
	Moderately
	Severely
	Extremely
	Too breathless to do these

11. Were you short of breath today when performing your usual activities outside the home such as yard work or errands?	Not at all
	Slightly
	Moderately
	Severely
	Extremely
	Too breathless to do these
12. Were you tired or weak today?	Not at all
	Slightly
	Moderately
	Severely
	Extremely
13. Last night, was your sleep disturbed?	Not at all
	Slightly
	Moderately
	Severely
	Extremely
14. How scared or worried were you about your lung problems today?	Not at all
	Slightly
	Moderately
	Severely
	Extremely
Copyright	EXACT© 2013, Evidera, Inc. All rights reserved. EXACT version 1.1-English (universal) 9/9/2009

\*The EXACT instrument and scoring program are owned by Evidera. The questions listed above may be displayed in another format as per the formal licensing agreement with the edairy vendor.

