- >20% decrease from the mean morning baseline FEV1 on more than 3 of the last 7 (rolling) days during Part 1 (commencing once the predose pre-bronchodilator

study qualifying FEV1 (ie, pre-PFT) is performed at the screening visit [visit 1]) or Part 2

- viral or bacterial respiratory infection during Part 2 which results in an increase in the symptoms of COPD from the patient's normal baseline level
- increase of  $\geq 2$  on the ER-S: COPD daily respiratory symptoms (RS) Total Score during Part 1 (commencing at the start of the screening period) or Part 2
- $\geq 12$  or more albuterol/salbutamol puffs per day on more than 2 of the last 7 (rolling) days during Part 1 (commencing at the start of the screening period) or Part 2

Other possible reasons for a patient discontinuing participation in the study may include:

- patient withdrew consent
- Sponsor requested patient to be withdrawn
- protocol deviation/noncompliance
- AE
- lack of efficacy
- lost to follow-up/failure to return
- pregnancy
- other (specify within eCRF)

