#### ediary/electronic flow meter

For the screening period, run-in period, Part 1 and Part 2 of the study, patients will be issued an ediary/electronic flow meter to record COPD symptom scores (EXACT); albuterol/salbutamol MDI usage; study medication usage (run-in and Part 2 only); and FEV1 measurements at home. Diary collection begins at the time of signing the ICF. eDiaries/electronic flow meters will be dispensed on the 1st day of the screening period prior to patients beginning any medication washout, to assist with safety monitoring throughout the screening period.

In addition device robustness data will be tracked via the ediary system.

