#### Screening Visit:

The stability limit established at the screening visit will be used to determine alert criteria for worsening COPD during the screening and run-in periods. The FEV1 stability limit at the screening visit will be calculated as follows:

Best pre-bronchodilator qualifying FEV1 measurement at the screening visit (visit 1) using the onsite spirometer  $\times 80\%$ .

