The ER-S: COPD (derived from the EXACT score) will be used to assess disease stability throughout the study. A baseline score will be obtained from the first available evening session after signing the ICF for use during the screening and run-in periods and from the latest available evening session before the randomization visit (visit 2) for use during the double-blind and open-label treatment periods. If at any time, there is increase in the ERS-COPD daily RS-Total score of  $\geq 2$  from baseline, the diary will alert the patient to notify the investigational center personnel to discuss the patient's current health status. The Investigator will need to determine if the patient is able to continue participating in the study as per the withdrawal criteria in [section 6.5](#).

Refer to [Appendix C](#) for additional details.

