The ER-S: COPD (derived from the EXACT score) will be used to assess disease stability throughout the study. A baseline score will be obtained from the first available evening session after the signing the ICF for use during the screening and run-in periods and from the latest available evening session before the randomization visit (visit 2) for use during the double-blind and open-label treatment periods. If at any time, there is increase in the ERS-COPD daily RS-Total score of ≥ 2 from baseline, the eDiary will alert the patient to notify the investigational center personnel to discuss the patient’s current health status. The Investigator will need to determine if the patient is able to continue participating in the study as per the withdrawal criteria.

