Appendix 2: EXACT DAILY DIARY

[figure not shown]
Instructions: Please complete your diary every evening, just before you go to bed. As you answer the following questions, please select the option that best describes your experience.

The eDiary will be programmed to display your ER-S: COPD daily respiratory symptoms (RS) Total score. A baseline score will be obtained from the first available evening session after the screening visit (visit 1) for use during the screening and run-in periods and from the latest available evening session before the randomization visit (visit 2) for use during the double-blind and open-label treatment periods. If at any time, there is increase in the daily RS Total score of ≥ 2 from baseline, the eDiary will alert you to notify investigational center personnel to discuss your current health status.

1. Did your chest feel congested today?	Not at all
	Slightly
	Moderately
	Severely
	Extremely
2. How often did you cough today?	Not at all
	Rarely
	Occasionally
	Frequently
3. How much mucus (phlegm) did you bring up when coughing today?	Almost constantly
	None at all
	A little
	Some
	A great deal
4. How difficult was it to bring up mucus (phlegm) today?	A very great deal
	Not at all
	Slightly
	Moderately
	Quite a bit
5. Did you have chest discomfort today?	Extremely
	Not at all
	Slight
	Moderate
	Severe
6. Did your chest feel tight today?	Extreme
	Not at all

Sponsor: Lupin Inc.
Protocol no: TB-DPI-301

	Slightly
	Moderately
	Severely
	Extremely
7. Were you breathless today?	Not at all
	Slightly
	Moderately
	Severely
	Extremely
8. Describe how breathless you were today:	Unaware of breathlessness
	Breathless during strenuous activity
	Breathless during light activity
	Breathless when washing or dressing
	Present when resting
9. Were you short of breath today when performing your usual personal care activities like washing or dressing?	Not at all
	Slightly
	Moderately
	Severely
	Extremely
	Too breathless to do these
10. Were you short of breath today when performing your usual indoor activities like cleaning or household work?	Not at all
	Slightly
	Moderately
	Severely
	Extremely
	Too breathless to do these
11. Were you short of breath today when performing your usual activities outside the home such as yard work or errands?	Not at all
	Slightly
	Moderately
	Severely
	Extremely
	Too breathless to do these
12. Were you tired or weak today?	Not at all
	Slightly
	Moderately
	Severely

Sponsor: Lupin Inc.
Protocol no: TB-DPI-301

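### The diary appendices of both documents take the screening symptom-score baseline after visit 1, although the body text and the alert rule need it from consent

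*Protocol*

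**What the plan says.** The baseline for the screening and run-in E-RS alert is defined in four places.

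- Protocol 9.2.2.6: "A baseline score will be obtained from the first available evening session after signing the ICF".
- SAP 9.10: "first available evening session after the signing the ICF".
- Protocol Appendix C: "A baseline score will be obtained from the first available evening session after the screening visit (visit 1").
- SAP Appendix 2: "first available evening session after the screening visit (visit 1").

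Protocol 6.5 does not define a baseline. It sets when the criterion of a 2-point rise applies, namely to the "Total Score during Part 1 (commencing at the start of the screening period) or Part 2". Protocol 9.3.1 says that screening starts when the consent form is signed, that most visit 1 procedures wait until washout is complete, and that visit 1 comes directly before run-in. Protocol 7.4 has the diary handed out on the first day of screening, "prior to patients beginning any medication washout, to assist with safety monitoring throughout the screening period".

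**The concern.** The alert compares each evening's RS-Total score with a baseline. Protocol 6.5 wants that comparison from the start of screening, and the appendix rule supplies no baseline until visit 1 has taken place. For a patient in washout these two points can be weeks apart.

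That interval is when maintenance therapy has been stopped, and it is the stated reason for dispensing the diary early. Appendix C is not background text. It is the diary specification, it tells patients when they will be alerted, and Protocol 9.2.2.6 sends the reader there for detail, so a diary vendor could plausibly have built from it.

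The run-in threshold may also differ, because one rule measures the baseline at consent and the other after washout.

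**Working it through.** The plan states no figure to reproduce. The check compares the texts and then works out timing from the stated study days.

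**1. Is the appendix wording current?** Yes. Both appendices are live text. The Amendment 1 summary (Protocol Appendix D) shows that 9.2.2.6 once carried the visit 1 wording and was deliberately moved to consent. The summary revises Appendices A and B, but the pages available show no matching change to Appendix C. The SAP was written against Amendment 1 and contains both rules.

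**2. Does a precedence rule settle it?** No. Protocol section 11 lets the SAP override the protocol, but the SAP contradicts itself here. That clause also sits in a section on statistical analysis, so it may not reach diary alerts at all.

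**3. Length of the gap.** Days without an E-RS alert under the appendix rule = day of visit 1 − day of consent. Assuming maintenance therapy stops on the day of consent, this equals the washout required in Protocol 5.1.1:

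| Prior therapy | Gap (days) |
|---|---|
| No washout, consent on the day of visit 1 | 0 |
| LABA alone | 7 |
| LAMA, alone or combined | 21 |
| ICS or ICS/LABA | 30, and at most 30 + 3 = 33 |

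The 30 days agree with the screening window in 9.3.1: day −44 to day −14 is 30 days.

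**4. Can the other numerical criteria in 6.5 cover the gap?** Four apply before randomization.

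- FEV1 more than 20% below the visit 1 predose value: needs visit 1.
- Rolling home FEV1: runs "during Part 1 (commencing once the predose pre-bronchodilator" qualifying measurement has been made at visit 1.
- E-RS rise of 2 or more: active from consent under the body text, inactive until after visit 1 under the appendices.
- Albuterol at 12 or more puffs a day on more than 2 of the last 7 days, so at least 3 days: active throughout.

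The FEV1 alert limit has the same dependence on visit 1 (9.2.1.1, Screening Visit): "The stability limit established at the screening visit will be used to determine alert criteria for worsening COPD". Criteria active before visit 1 therefore number 2 under the body text (E-RS, albuterol) and 1 under the appendix text (albuterol).

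**5. Effect on the run-in threshold.** An illustration with assumed scores: if RS-Total is 10 at consent and 14 after visit 1, the run-in alert fires at 10 + 2 = 12 under the body text and at 14 + 2 = 16 under the appendix text. The documents give no data on how scores move during washout.

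**6. What is unaffected?** The baseline for the double-blind and open-label periods is the last evening entry before visit 2 in all four places. E-RS values are only listed (SAP 13.7.8).

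**The case against.** The strongest reply is that this is leftover wording. The body text of both documents agrees, the amendment shows a deliberate change, and nothing shows that the diary was built from the appendix. This stands in part: the intended rule is clear, and the loss of alerts is conditional on a configuration that cannot be seen from the documents. It does not remove the contradiction in a text that specifies the diary.

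Second, visit 1 may be read more loosely. Footnote 5 of the Schedule of Events lets it span several days, and 9.3.1 lists consent and diary dispensing among its procedures. If visit 1 begins at consent, the two rules nearly coincide. But the same footnote and 9.3.1 hold back the remaining procedures until washout is complete and place visit 1 directly before run-in. The table above is therefore an upper case on the stricter reading.

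Third, other safeguards remain. Symptom scores and home FEV1 are still recorded daily, adverse events and exacerbations are collected from consent, and 6.5 also lists disallowed respiratory medication and respiratory infection. This is correct: only the automated E-RS comparison is lost. However, adverse events and exacerbations are captured by interview at visits or calls, and the schedule shows no call between consent and visit 1.

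Fourth, the correction comes late. The SAP already reports an interim analysis planned for when 150 patients had completed Part 1, and their screening cannot be changed. The sponsor then planned about 378 randomized patients instead of 240, which is 378 − 240 = 138 more. The number still to be screened is not stated, so the practical benefit is uncertain.

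**Conclusion.** The concern holds. Each document gives two incompatible rules for the screening and run-in E-RS baseline, and the appendix rule cannot support the alert start required by Protocol 6.5.

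If the diary follows the appendices, the alert is absent for up to 7, 21 or 30 to 33 days depending on prior therapy. This assumes that therapy stops at consent and that visit 1 follows washout. The gap is shorter on a looser reading of visit 1, and zero if the diary already follows the body text.

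This is a matter of safety monitoring before randomization. It should be corrected, but it does not bear on the bioequivalence conclusion, the superiority tests or the sample size.

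**What to change.** In Protocol Appendix C and SAP Appendix 2, replace the reference to the screening visit with *after signing the ICF*, so that they match Protocol 9.2.2.6 and SAP 9.10. Ask the diary vendor to confirm in writing which evening entry sets the screening baseline, and correct the configuration if it is tied to visit 1.

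The text change is one phrase in each appendix. Protocol 12.2 requires an approved amendment for any protocol change, so Appendix C can be corrected with the next amendment, and the SAP appendix when SAP2 is finalized before database lock. The configuration check need not wait for either, and it is the step with practical value for patients still to be screened.

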## APPENDIX D: PROTOCOL AMENDMENT 1 SUMMARY OF CHANGES

Protocol Amendment 1 incorporates the following changes. The revisions listed below have been made to the protocol and synopsis as appropriate, and are considered substantial. Revised or new text is presented in bold italics and deletions are struck through. Minor typographical and formatting errors were corrected throughout the protocol.

The primary reasons for this amendment are:

- To incorporate the administrative letter dated 27 Feb 2017, Clarification of the roles of the unblinded/blinded study personnel during study medication administration in Part 1, updates to the study medication and In-Check DIAL instructions for use, and clarification of clinical laboratory results prior to run-in.
  - Roles of the unblinded/blinded study personnel: Unblinded study personnel will prepare double-blind study medication and dispense the inhalers to blinded study personnel and observe dose administration in Part 1. Blinded study personnel will perform study medication training during all parts of the study
  - In-Check DIAL: A new release of the In-Check DIAL device was issued prior to study initiation (ie, new dial top developed to group inhalers by resistance instead of device type); therefore, updated the instructions for use accordingly.
  - Clinical laboratory results: Based on the study visit schedule, the clinical laboratory results may not be available prior to a patient entering run-in; therefore, footnote #5 in the Schedule of Events was updated to state the results must be available and evaluated prior to randomization.
- To incorporate the administrative letter dated 10 Mar 2017, Clarification of the dispensation of the ed diary/electronic flow meter and safety monitoring during the screening period.
  - Ed diary: Diary collection will begin at the time of signing the ICF. COPD symptom scores (EXACT), albuterol/salbutamol MDI usage, and once daily (morning) FEV1 measurements at home using will be collected using the ed diary/electronic flow meter during the screening period.
  - Screening period/screening visit assessments: The screening period may occur up to 30 days prior to the start of the run-in period. Procedures for the screening visit (visit 1), with the exception of signing of the ICF, assigning a patient number, performing a pre-washout physical examination, and dispensing/completing the ed diary, cannot occur until appropriate medication washouts have been completed in accordance with the study protocol.
- To prohibit caffeine-containing medication for at least 6 hours prior to spirometry assessments at any scheduled visit (visit 1 through visit 4).

### Study Centers, Synopsis (page 8)

#### Original text:

The study is planned to be conducted at approximately 60 investigational centers in the United States of America (USA). Additional centers in the USA may be added as needed.

#### Revised text:

The study is planned to be conducted at approximately ~~60~~ 40 investigational centers in the United States of America (USA). Additional centers in the USA may be added as needed.

**Rationale for change:** *Based on enrollment projections, 40 investigational centers were selected to participate in the study.*

### Study Design Overview, Synopsis (page 9) and Section 5.1.1 Part 1: Double-Blind Treatment Period (page 26)

#### Original text:

The screening period, of up to 30 days, allows for adequate washout of the following COPD therapies, along with other prohibited medications per protocol:

- long-acting anti-muscarinic agent (LAMA) medications (including mono products and combination products containing LAMAs [eg, LAMA/LABA]) will not be permitted within 21 days of the screening visit (visit 1)
- long-acting beta agonist (LABA) mono products will not be permitted within 7 days of the screening visit (visit 1)
- inhaled corticosteroid (ICS) mono products and ICS/LABA combination products will not be permitted within 30 days of the screening visit (visit 1)

#### Revised text:

The screening period, of up to 30 days, allows for adequate washout of the following COPD therapies, along with other prohibited medications per protocol:

- long-acting anti-muscarinic agent (LAMA) medications (including mono products and combination products containing LAMAs [eg, LAMA/LABA]) will not be permitted within 21 days of the screening visit (visit 1)
- long-acting beta agonist (LABA) mono products will not be permitted within 7 days of the screening visit (visit 1)
- inhaled corticosteroid (ICS) mono products and ICS/LABA combination products will not be permitted within 30 days of the screening visit (visit 1)

***If a patient is washing out of ICS (monotherapy) or ICS/LABA combination therapy as stated above, an additional 3 day window is permitted to complete the assessments for the screening visit (visit 1).***

**Rationale for change:** *For patients on ICS (monotherapy) or ICS/LABA combination therapy additional time may be needed to complete all screening assessments prior to the run-in period; therefore, the window has been extended.*

